11.3. Study Visits

Unless indicated otherwise, all subjects are expected to complete all scheduled study assessments/procedures, regardless of treatment assignment.

11.3.1. Screening

Subjects with C3G, IgAN, or PMN who may require additional treatment to an ACEi or ARB may be screened for this study.

Written consent must be obtained from the subject as required by national or local law and institutional practice, prior to conducting any study-related assessments/procedures. Signing of the informed consent form (ICF) may occur prior to the first on-study visit, which is defined as the visit where site-conducted screening procedures are first performed.

A 56-day window is provided to qualify subjects for the study. All screening procedures do not need to be completed on the same day, but all screening procedures must be completed, and the results reviewed and approved by the investigator (or designee) prior to dosing a subject. The screening period can be extended up to 28 additional days with approval by the medical monitor (or designee) on a case-by-case basis.

The investigator (or designee) will conduct the following assessments at the screening visit(s), including:

- Signing of the ICF
- Review of inclusion and exclusion criteria
- Demographic information
- Medical and medication history including confirmation of adequate vaccination and either providing protocol required vaccinations or scheduling with local health care provider to vaccinate prior to Baseline (Day 1); see Section 12.2.1.
- Disease Specific Medical History Form
- 12-lead ECG
- Vital signs (blood pressure, temperature, and pulse rate)
- Complete physical examination
- Height/weight/body mass index (BMI) calculation
- Serum pregnancy test for female subjects of childbearing potential
- Blood collection for FSH for any woman post-menopausal for ≥ 12 months and ≤ 2 years (FSH measurement is not needed at screening to confirm postmenopausal state in women who report no menses for > 2 years)
- Blood collection for clinical chemistry, hematology, coagulation, and PD biomarkers
- Blood collection for HBV, HCV, HIV, and VZV serology
- Single void collection for urinalysis including microscopy and drugs of abuse screen

- Recording of prior medications within 30 days prior to first dose and current medications
- Provide collection containers with instructions for collection and return of an intended 24-hour urine sample to the clinic during screening and, if applicable, at the Day 1 Visit
- Register the subject in Interactive Response Technology (IRT)
- After confirmation that all other study eligibility criteria are met (including intended 24-hour uPCR criterion), a percutaneous needle biopsy of the kidney per local practice and guidelines will be required, unless a kidney biopsy with digital images and a pathology report are available within 3 months of the screening visit with C3G or 6 months of the screening visit with IgAN or PMN that meets all protocol requirements and is confirmed by the medical monitor and central pathologist

Note: The central pathologist will determine eligibility by confirmation of the primary diagnosis of either C3G, IgAN, or PMN and active disease prior to the Day 1 Visit and first dose of BCX9930

A screening failure eCRF page will be completed for those subjects who do not proceed with study dosing, recording the reason for screening failure.

11.3.2. Rescreening/Retesting

Rescreening of ineligible subjects, where there is a reasonable expectation that the subject will become eligible, is permitted. If a subject is unable to be qualified in the 56-day window, eg, due to a dose change of an ACEi/ARB or acute illness or retesting of screening labs or delays related to screening biopsy, the screening window may be extended up to 28 additional days with the approval of the sponsor medical monitor (or designee). Retesting of specific assessments without entirely rescreening a subject may be permitted with the approval of the sponsor medical monitor (or designee).

11.3.3. Baseline Visit (Day 1)

For subjects participating in the PK/PD substudy, please refer to Table 2 and Table 4 for procedures and timings.

Before any study drug is administered, the following assessments will be completed:

• Administration of questionnaires:

- Review of inclusion and exclusion criteria and prohibited medications
- Review of medical and medication history
- Review of Disease Specific Medical History Form
- Weight and BMI

- 12-lead ECG (triplicate ECGs)
- Vital signs (blood pressure, temperature, and pulse rate)
- Complete physical examination
- Single void urine collection for urinalysis including microscopy and biomarkers
- A urine pregnancy test for female subjects of childbearing potential. A negative urine pregnancy result must be recorded in order for the subject to receive study drug.
- Blood collection for clinical chemistry, hematology, coagulation, and PD biomarkers
- Review concomitant medications and AEs
- Provide collection container with instructions and return of an intended 24-hour urine sample
- Study drug dispensing (via IRT)

Where possible, the questionnaires should be completed by the subject prior to other assessments to prevent influencing subject perceptions.

11.3.4. On-study Visits (Weeks 1, 2, 4, 8, 12, 16, 20, 24, 28, 32, 36, 40, 44, 48, and 52)

Subjects will return to the clinic during Week 1 (Day 8 ± 1 day), Week 2 (Day 15 ± 1 day), Week 4 (Day 29 ± 1 day), Week 8 (Day 57 ± 3 days), Week 12 (Day 85 ± 3 days), Week 16 (Day 113 ± 3 days), Week 20 (Day 141 ± 3 days), Week 24 (Day 169 ± 3 days) Week 28 (Day 197 ± 3 days), Week 32 (Day 225 ± 3 days), Week 36 (Day 253 ± 3 days), Week 40 (Day 281 ± 3 days), Week 44 (Day 309 ± 3 days), Week 48 (Day 337 ± 3 days), and Week 52 (Day 365 ± 3 days).

At the Week 24 Visit, the clinical benefit of BCX9930 treatment will be assessed by the investigator. Subjects who are assessed as deriving clinical benefit will continue treatment up to Week 52. Subjects who continue BCX9930 treatment will complete study visits and assessments through the Week 52 Visit.

Subjects do not need to withhold any doses on clinic days or take a dose in the clinic, unless the clinic visit falls during the subject's normal time of dosing or PK/PD substudy procedures are also being conducted. PK/PD substudy visits for participating subjects should be scheduled such that the subject's normal dosing time occurs during the clinical visit, if possible. On these days, subjects should be instructed not to take their dose of BCX9930 until they are in clinic and the pre-dose PK and PD samples have been collected.

For subjects participating in the PK/PD substudy, please refer to Table 4 for procedures and timings.

The following assessments will be performed:

• Administration of questionnaires. Where possible, the questionnaire should be completed by the subject prior to other assessments:

- at Weeks 8, 12, 16, 20, 24, 36, and 52 only (or at the safety FU, if applicable)
- at Weeks 8, 12, 16, 20, 24, 36, and 52 only (or at the safety FU, if applicable)
- at Week 24 Visit for C3G only, Week 36 Visit for IgAN only, and
 Week 52 for PMN only (or at the safety FU, if not previously administered as described)
- at Week 24 Visit for C3G only, Week 36 Visit for IgAN only, and
 Week 52 for PMN only (or at the safety FU, if not previously administered as described)
- 12-lead ECG
- Vital signs (blood pressure, temperature, and pulse rate)
- Targeted physical examination (ie, symptom-driven, targeted to new signs and symptoms)
- Weight and BMI (not performed at the Week 1 and Week 2 Visits)
- Single void urine collection for urinalysis including microscopy, PK and biomarkers
- A urine pregnancy test for female subjects of childbearing potential
- Blood collection for clinical chemistry, hematology, coagulation, and PD biomarkers
- Blood collection for sparse PK plasma sample and documentation of time of sample collection, food status and the time of the last two doses of study drug taken
- Review/capture of concomitant medications and AEs
- Assessment of the clinical benefit of BCX9930 (at the Week 24 Visit only)
- Provide collection container with instructions and return of an intended 24-hour urine sample
- Study drug dispensing (via IRT) and accountability, as per Table 2 and Table 3

A percutaneous needle biopsy of the kidney per local practice and guidelines will be performed at Week 24 for subjects with C3G. An optional percutaneous needle biopsy of the kidney can be performed at Week 36 for subjects with IgAN or at Week 48-52 for subjects with PMN if a subject consents for the optional procedure. The biopsy should be scheduled during the specified visit after completion of all other assessments or within the timeframe after the visit as specified in Section 12.4.2, but may not be performed prior the specified visit. For subjects with PMN, if the biopsy procedure is performed after the Week 52 Visit, the subject will continue dosing until the day of the biopsy procedure and study drug return and accountability will occur on the date of the biopsy procedure.

All subjects who sign a separate informed consent will participate in exploratory pharmacogenomics testing at a single visit from Day 1 up to the Week 24 Visit (including the Safety FU Visit, if applicable).

11.3.5. Additional Assessments for Renal and Hepatic Safety Monitoring

Additional assessments to monitor for potential renal and hepatic toxicity will be performed at Week 3 (Day 22 ± 1 day), Week 5 (Day 36 ± 3 day), Week 6 (Day 43 ± 3 day), Week 7 (Day 50 ± 3 day), and Week 10 (Day 71 ± 3 day). The assessments may be performed at the investigative site, at a local laboratory more convenient for the subject, or via a home health service (where permitted and available) and will be continued until sufficient data are available to allow for reduction or elimination of the additional assessments.

The minimum procedures to be completed at each assessment will depend on whether the subject is assessed at the investigative site or assessed at non-investigative site.

For subjects assessed at the investigative site:

- Review/record AEs, concomitant medication use
- Vital signs (blood pressure, temperature, and pulse rate)
- Blood collection for clinical laboratory evaluations:
 - Clinical chemistry
- Blood collection for PK
- Urine collection for clinical laboratory evaluations:
 - Urinalysis including microscopy
 - Urine for biomarker testing
- Urine collection for PK

The above assessments will also be performed for subjects identified with potential renal or hepatic events who are required to return to the investigative site (Section 13.5).

For subjects assessed at non-investigative sites:

- Blood collection for clinical laboratory evaluations:
 - Clinical chemistry (to include at a minimum: sCr, eGFR, blood urea nitrogen [BUN], ALT, AST, ALP, and bilirubin [total and direct])
- Urine collection for clinical laboratory evaluations:
 - Urinalysis (to include at a minimum specific gravity, pH, protein, and blood)
 - Urine microscopy (only if the facility is deemed sufficiently qualified to perform this analysis)
 - Urine albumin to creatinine ratio (uACR)

The enhanced safety assessments described in this amendment (ie, the additional assessments to be completed during the first 12 weeks of BCX9930 therapy) will be revisited and reviewed with the DMC after an additional approximately 15 subjects have completed through at least the first 8 weeks of monitoring across the BCX9930 program.

11.3.6. Safety follow-up Visit

All subjects will return to the clinic approximately 4 weeks (28 ± 3 days) after the date of their last dose of BCX9930 for safety assessments.

The following assessments will be performed:

 Administration of questionnaires. Where possible, the questionnaire should be completed by the subject prior to other assessments (for early discontinued subjects only):

- 12-lead ECG
- Vital signs (blood pressure, temperature, and pulse rate)
- Targeted physical examination (ie, symptom driven, targeted to new signs and symptoms)
- Weight and BMI
- Single void urine collection for urinalysis including microscopy, and biomarkers
- Blood collection for clinical chemistry, hematology, coagulation, and PD biomarkers
- A urine pregnancy test for female subjects of childbearing potential
- Review and capture of concomitant medications and AEs
- Collection of intended 24-hour urine sample with the number of days between last dose and collection documented
- Study drug accountability

12. STUDY ASSESSMENTS

12.1. Chronology of Assessments

The following chronology of events should be adhered to during the scheduled visits, as applicable:

- Subject questionnaires: obtain prior to other study procedures
- ECGs: obtain prior to vital signs and urine specimen collection
- Vital signs: obtain prior to urine specimen collection
- Urine collection: obtain prior to blood collection

• Blood collection

It is preferred that the patient-reported outcomes (PRO) questionnaires be administered prior to completing other study procedures, and clinic procedures, such as ECGs, physical examinations, and vital signs measurements, should be completed prior to any blood collection.

12.2. Demographic/Medical History

Demographic information and medical and medication history will be captured for each subject participating in the study at the Screening Visit. Medical history, medication review, and review of inclusion and exclusion criteria, potentially nephrotoxic medications, and prohibited medications will also be updated and rechecked at baseline (Day 1) as outlined in Section 11.3.3.

A Disease Specific Medical History Form including baseline C3G, IgAN, or PMN clinical characteristics and disease burden including prior genetic screening for complement-related mutations, nephritic factors, or other disease characteristics, clinical labs (eg, serum creatinine), and copies of pathology reports with WSIs (if available) will be captured during screening. Medication history will include details of C3G, IgAN, or PMN treatments administered (including plasma exchange therapy and other investigational product).

12.2.1. Vaccination Requirements

BCX9930 blocks the alternative pathway of complement activation; therefore, subjects may have increased susceptibility to bacterial infections, especially infections with encapsulated organisms such as *N. meningitidis*, *S. pneumoniae*, and *H. influenzae*, but also with unencapsulated strains of *N. meningitidis* and other bacteria such as *N. gonorrhoeae*. Effective and current vaccination coverage must be documented for *N. meningitidis* Types A, C, W, and Y, and for *S. pneumoniae*. Vaccination for *N. meningitidis* Type B and for *H. influenzae* (Hib) is strongly encouraged where authorized and available.

For those who have not received all of the required vaccines (including boosters) or vaccine series, administration of any needed vaccines should start no later than 14 days prior to Day 1. If the recommended vaccination coverage requires more than a single dose, then the additional dose(s) may be administered after Day 1 to complete the recommended vaccination coverage. If a vaccine is not available, the sponsor medical monitor (or designee) should be contacted to discuss potential options in order to satisfy eligibility requirements prior to completing the Day 1 visit. Appropriate antibiotics for prophylaxis may be given during the study in accordance with local standard of care and any relevant vaccination guidance (see Section 9.1).

Unless local guidelines are more stringent, the Advisory Committee on Immunization Practices (ACIP) recommendations for meningococcal vaccination and ACIP guidance for altered immunocompetence (including complement inhibition therapy) should be followed (Mbaeyi, Pondo et al. 2020). For vaccines against serogroups A, C, W, and Y, a booster vaccine should be given every 5 years while on complement inhibitor therapy; the available vaccines are interchangeable. For vaccines against serogroup B, a booster vaccine should be given 1 year after the series completion and every 2 to 3 years thereafter; the available vaccines are not interchangeable (Mbaeyi, Pondo et al. 2020).

S. pneumoniae vaccination is also required; vaccination with both conjugate and polysaccharide vaccines is preferred.

Vaccination or a booster vaccine against Hib is strongly encouraged for all study participants where authorized and available.

Investigators should review each subject's vaccination status at periodic intervals to ensure that any needed booster vaccinations are administered at the optimal timing during the study. Please contact the sponsor medical monitor or designee for any questions.

If a patient receives a SARS-CoV-2 vaccination, this should be captured as a prior or concomitant medication entry. Vaccinations that require more than one inoculation should have a separate prior or concomitant medication entry for each injection.

If patient experiences any AEs related to SARS-CoV-2 vaccination, or any AE in temporal relation to the vaccination, these should be entered on the adverse events page.

If a live vaccine needs to be given during the study, including after screening visit, please contact the sponsor medical monitor or designee.

12.4. Efficacy/Effectiveness Assessments

12.4.1. Intended 24-hour Urine Collection

An intended 24-hour urine collection will be required prior to each clinic visit except for the initial Screening Visit. All subjects will receive a container and patient instructions for the collection and return of an intended 24-hour urine sample that will be initiated out of the clinic. After completion of the intended 24-hour collection, the sample will be returned to the clinic. A phone call to remind subjects to complete the intended 24-hour collection will be conducted within a week prior to the scheduled visit. Urine samples are intended to be collected over a 24-hour period and intended 24-hour samples will be accepted even if there are reports of missing a single void collection.

An aliquot from 24-hour urine collections may be reserved for analysis of the urine concentration of BCX9930 and metabolites.

12.4.2. Percutaneous Needle Biopsy of the Kidney

After confirmation that all other study eligibility criteria are met during screening per local practice and guidelines:

• Subjects will undergo a percutaneous needle biopsy of the kidney during screening

Note: The screening biopsy procedure may be waived with approval of the central pathologist and agreement with the medical monitor for any subject who has undergone a renal biopsy procedure within 3 months prior to initiating screening with C3G, and within 6 months prior to initiating screening with IgAN or PMN, provided that required materials are adequate for pathology evaluation per protocol procedures

An on-treatment, percutaneous needle biopsy of the kidney will be performed at the following visit after completion of all other assessments, or during the specified times below by treatment cohort:

- Week 24 or within 7 days after the visit for subjects with C3G
- Week 36 or within 7 days after the visit for subjects with IgAN (optional)
- Week 48 to within 3 days after the Week 52 Visit for subjects with PMN (optional)

The on-treatment biopsy is required for subjects with C3G but is optional for subjects with IgAN or PMN. For subjects with PMN, if the biopsy is scheduled after the Week 52 Visit, then dosing with BCX9930 will continue until the day of the procedure. Protocol-specified, on-treatment biopsies will not be required for subjects who are discontinued from BCX9930 treatment.

12.4.2.1. Central Pathologist

A pathology manual of procedures will be provided to sites with study-specific methods regarding specimen processing, scanning, capture of morphologic/morphometric features, computer assessment, and data collection. Each investigator should review the pathology manual of procedures with an experienced, on-site renal pathologist.

Renal biopsy samples will be processed locally according to the pathology manual. Images (WSIs of the light microscopy, digital IFs or IHCs, and digital EMs), and details from the local pathology report will be reviewed by the central pathologist for confirmation of a protocol defined diagnosis of C3G, IgAN, or PMN based on the following inclusion criteria:

• **C3G:** a sole or dominant glomerular IF or IHC staining for C3 of at least two orders of magnitude greater intensity than for any other immunoreactant (D'Agati and Bomback 2012).

Evidence of disease activity as follows:

- C3GN with at least 25% of glomeruli with at least segmental mesangial and segmental endocapillary hypercellularity.
- DDD with at least 2 of the following 3:
 - at least 25% of glomeruli with segmental mesangial hypercellularity
 - at least 25% of glomeruli with segmental endocapillary hypercellularity
 - at least one active crescent

A minimum of 4 patent glomeruli between the light microscopy and EM thick section WSIs is required. At least one patent glomerulus is required for IF or IHC digital images.

- IgAN: IF or IHC staining for IgA and C3, with dominant IgA compared to other Igs/immunocomplexes. Disease activity required with M1 and E1 and/or C1, including active crescents and/or necrosis as per Oxford IgA scoring (Haas, Verhave et al. 2017, Trimarchi, Barratt et al. 2017). A minimum of 8 patent glomeruli between the light microscopy and EM thick section WSIs is required. At least one patent glomerulus is required for IF or IHC digital images.
- PMN: IF or IHC capillary wall granular staining for IgG and C3 with at least 50% of the deposits being active Ehrenreich and Churg stage I and/or II by EM; stage III deposits are allowed (Ehrenreich and Churg 1968). Active crescents ≤ 10% are allowed. A minimum of 6 patent glomeruli between the light microscopy and EM thick section WSIs is required. At least one patent glomerulus is required for IF or IHC digital images.
- All: Images for LM, IF or IHC, and EM are of sufficient quality to allow for interpretation and diagnosis
- All: $\leq 50\%$ global glomerulosclerosis
- All: < 50% tubulointerstitial fibrosis
- C3G and IgAN: $\leq 50\%$ active crescents

The WSIs of LMs, digital IFs or IHCs, digital EMs, and report findings for study eligibility will also serve as the pre-treatment baseline for change from baseline comparisons to the ontreatment biopsies by the central pathologist. In addition, unstained EM grids will be shipped from sites to the central pathologist for additional baseline EM assessments and reporting if a biopsy is performed during the screening period. For a biopsy performed prior to the screening, unstained EM grids may be shipped to the central pathologist if available.

If other biopsies not specified per protocol are performed during the study, the available images (WSIs of the light microscopy, digital IFs or IHCs, and digital EMs) and details from the local pathology report will be reviewed by the central pathologist, if available.

12.4.3. For the PMN cohort only, will be measured at Screening, Baseline, and every 4 weeks until Week 52.

[figure not shown]

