6.2.2. Secondary Endpoints

The secondary endpoints of this study are:

- Number and proportion of subjects with a uPCR response defined as:
 - Partial remission, $\geq 50\%$ reduction from baseline
 - Complete remission, $\leq 500 \text{ mg/g}$
 - Normalization, $\leq 200 \text{ mg/g}$
- Change from baseline in 24-hour urinary protein excretion as measured by percentage change in urinary protein from baseline
- Change from baseline in eGFR
- Change from baseline in serum albumin
- Number and proportion of subjects with the following parameters:
 - Protein \geq 3.5 g in a 24-hour urine collection
 - Serum albumin $\leq 2.5 \text{ g/dL}$
- Number and proportion of subjects with a morphologic response in each of the following categories (C3G cohort only at Week 24):
 - Decreased endocapillary hypercellularity, mesangial hypercellularity, active crescents (if present), glomerular leukocyte infiltration, fibrinoid necrosis, membranoproliferative glomerulonephritis pattern
 - Decreased acute tubular injury, interstitial inflammation, interstitial edema
 - Reduction in C3 glomerular staining
 - Reduction in the extent of deposits, clearing of deposits, or no additional active deposits as assessed by electron microscopy (EM)
 - No progression of chronic changes (ie, global, segmental glomerulosclerosis, tubular atrophy/interstitial fibrosis, arteriosclerosis)
- Number and proportion of subjects with a TEAE
- Number and proportion of subjects who discontinue due to a TEAE
- Number and proportion of subjects who experience a treatment-emergent serious adverse event (TESAE)
- Number and proportion of subjects who experience a Grade 3 or 4 TEAE based on Common Terminology Criteria for Adverse Events (CTCAE)
- Number and proportion of subjects who experience a CTCAE treatment-emergent Grade 3 or 4 laboratory abnormality

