9.4. Randomization and Blinding

This is an open-label, non-randomized study. No study treatments will be blinded or masked.

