Each eligible subject who consents to participate in the study will receive up to 52 weeks of BCX9930. All subjects will be required to attend at least 9 in-clinic study visits through 24 weeks: Day 1 (Baseline), Week 1 (Day 8), Week 2 (Day 15), Week 4 (Day 29), Week 8 (Day 57), Week 12 (Day 85), Week 16 (Day 113), Week 20 (Day 141), and Week 24 (Day 169) and 5 additional safety assessments visits at Weeks 3 (Day 22), Week 5 (Day 36), Week 6 (Day 43), Week 7 (Day 50), and Week 10 (day 71), either at the investigative site, at a local laboratory more convenient for the subject or via a home health service (where permitted and available). At the Week 24 Visit, the clinical benefit of BCX9930 treatment will be assessed by the investigator. Subjects who are assessed as deriving clinical benefit will continue treatment up to Week 52 and be required to attend at least 7 additional in-clinic visits: Week 28 (Day 197), Week 32 (Day 225), Week 36 (Day 253), Week 40 (Day 281), Week 44 (Day 309), Week 48 (Day 337), and Week 52 (Day 365). All subjects will return to the clinic approximately 4 weeks (28 ± 3 days) after the date of their last dose of BCX9930 for the safety FU Visit.

An on-treatment, percutaneous needle biopsy of the kidney will be performed for subjects with C3G at a specified visit after completion of all other assessments, or during the specified times as described in Section 12.4.2. The on-treatment biopsy is optional for the IgAN and PMN cohorts. All subjects who undergo kidney biopsy should remain on study drug at least until the day of biopsy. Digital images and details from the local pathology reports from the on-treatment biopsies will be reviewed by the central pathologist to evaluate and describe changes from the baseline, pre-treatment digital images.

Protocol BCX9930-211

Version 4.0: 04 August 2022

An optional serial PK/PD substudy will include subjects who provide consent from each of the 3 cohorts to evaluate the PK and PD of BCX9930 at the Day 1 Visit and/or at a subsequent visit prior to the Week 24 Visit. Serial sampling of urine and blood will be performed over a period of 6 hours. Subjects who do not participate in the Baseline (Day 1) PK/PD sample collection are eligible to participate at a subsequent clinic visit prior to the Week 24 Visit.

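### C3G morphologic endpoint: the qualifying biopsy read doubles as baseline and no masking of time point is specified, so *decreased* can be favoured without a drug effect, by chance only for the entry features

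*Protocol*

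**What the plan says.** **Baseline.** Protocol 12.4.2.1 states that the eligibility images and "report findings for study eligibility will also serve as the pre-treatment baseline for change from baseline comparisons". The baseline is therefore both the stored images and the findings that admitted the subject.

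**Entry floor.** The same section requires disease activity. The C3GN criterion is "C3GN with at least 25% of glomeruli with at least segmental mesangial and segmental endocapillary hypercellularity". DDD needs two of three: at least 25% of glomeruli with mesangial hypercellularity, at least 25% with endocapillary hypercellularity, or at least one active crescent. Four patent glomeruli are enough. There are also upper limits on global sclerosis, tubulointerstitial fibrosis and (C3G and IgAN) active crescents.

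**Endpoint.** Protocol 6.2.2 counts C3G responders at Week 24 in five morphologic categories. The first is a decrease in features that include endocapillary and mesangial hypercellularity and crescents. It sets no minimum size of decrease and asks for no count of worsening.

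**Reading.** Under Protocol 11.1 the on-treatment images and local report details are "reviewed by the central pathologist to evaluate and describe changes from the baseline, pre-treatment digital images". At entry, too, "details from the local pathology report will be reviewed by the central pathologist for confirmation of a protocol defined diagnosis". On masking, Protocol 9.4 says only "This is an open-label, non-randomized study. No study treatments will be blinded or masked".

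**Current analysis.** SAP 2 records two treated subjects. SAP 9 summarises 24-hour uPCR, 24-hour protein excretion and eGFR, and lists all other efficacy data. Pathology scores go to Listing 16.2.6.2.

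**The concern.** Two separate mechanisms can produce an apparent decrease without any drug effect.

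1. **Reader expectation.** A pathologist asked to describe change from a pre-treatment image in an open-label study may lean towards improvement. Nothing in the protocol or SAP guards against this.
2. **Selection on the baseline value.** A subject enters only if the qualifying biopsy reaches the floor. If that biopsy is also the baseline, a biopsy that happened to sample more affected glomeruli gets in, and one that sampled fewer does not. The next biopsy tends to look milder.

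There is no control group, so neither can be separated from a treatment effect. Protocol 5.4.1 intends these changes to inform later study designs, and a responder proportion with an unstated chance rate is a poor basis for that.

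**Working it through.** The plan gives no null response rate or sample-size calculation for this endpoint, so there is no figure of its own to reproduce. The check is on direction and size for one entry feature, with no drug effect and no reader effect.

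**Inputs from the documents:** floor of 25% of glomeruli; minimum of 4 glomeruli (stated for eligibility only); about 14 subjects per cohort.

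**Assumptions, because the documents give neither:** n = 4, 8 or 15 glomeruli at both biopsies; true affected fraction p ~ Beta(a, b), the same at both biopsies.

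**Model.** Affected counts x (baseline) and y (follow-up) are independent Binomial(n, p), so

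P(x, y) = C(n,x) · C(n,y) · B(a+x+y, b+2n−x−y) / B(a, b).

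Condition on x/n ≥ 0.25, then compare P(y < x) with P(y > x).

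**Hand check, n = 4, p fixed at 0.3.** The floor means at least one affected glomerulus.
- P(x = 0) = 0.7⁴ = 0.240, so P(qualify) = 0.760.
- P(tie) = 0.240² + 0.412² + 0.265² + 0.076² + 0.008² = 0.303. Without selection each direction has (1 − 0.303)/2 = 0.349.
- A subject with x = 0 cannot decrease, so after selection P(decrease) = 0.349/0.760 = 45.9%.
- Selection removes P(x = 0, y > 0) = 0.240 × 0.760 = 0.182 from the increases: (0.349 − 0.182)/0.760 = 21.9%, after rounding at the end.

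**Across assumed distributions.** Each cell shows % decreased / % increased after selection, then % each way without selection.

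| True activity | n = 4 | n = 8 | n = 15 |
|---|---|---|---|
| Beta(1,2) | 44.5 / 24.5; 29.7 | 47.9 / 30.2; 35.0 | 49.6 / 34.5; 38.8 |
| Beta(2,3) | 42.5 / 26.8; 33.4 | 46.3 / 32.0; 38.2 | 48.6 / 35.7; 41.4 |
| Beta(1,1) | 37.1 / 26.0; 29.7 | 41.2 / 31.8; 35.0 | 43.9 / 36.1; 38.8 |
| Beta(2,2) | 38.9 / 28.6; 33.4 | 43.0 / 34.1; 38.2 | 45.7 / 37.7; 41.4 |
| Beta(4,2), high activity | 33.9 / 30.5; 32.6 | 38.7 / 36.2; 37.6 | 41.9 / 39.9; 41.0 |

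Over the first four rows:
- Smallest excess of *decreased* due to selection: 45.7 − 41.4 = 4.3 points, or 14 × 0.043 = 0.6 subjects.
- Largest: 44.5 − 29.7 = 14.8 points, or 14 × 0.148 = 2.1 subjects.

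Under Beta(4,2) the excess is 0.9 to 1.3 points.

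**Sensitivity to true activity, n = 10, fixed p.** At p = 0.3, 59.2% decreased against 20.9% increased (40.3% each way without selection). At p = 0.7, 40.4% against 40.2%.

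**Opposite direction.** For a chronic feature capped at 50% at entry, with a Beta of mean 0.3 and concentration 4 (a + b = 4) and n = 10, 40.2% increase and 31.8% decrease. Selection there works against *no progression*.

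**The case against.** **The reader may be masked.** A reader might infer that the central pathologist is known to see the biopsy order. No sentence says so. Protocol 9.4 concerns treatment, and "to evaluate and describe changes from the baseline, pre-treatment digital images" describes a comparison, not how images are labelled. Protocol 12.4.2.1 refers feature capture and data collection to a pathology manual that is not among the documents. This stands: what can be said is that neither document specifies masking.

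**Selection does not touch every category.** A reader might extend the chance effect to the whole endpoint. Acute tubular injury, interstitial inflammation and edema have no entry floor, nor does the extent of deposits on EM in C3G, and for chronic changes the caps push the other way. This also stands.

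**Most of the 37–50% is symmetric noise.** It is tempting to read that range as the size of the bias. Without selection, 30–41% would already show a decrease; only the difference is due to selection.

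**A re-read does not cure the simulated asymmetry.** The model contains tissue sampling only, so masking removes none of it. Correct; masking addresses expectation and read error, which the documents give no means to size.

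**The baseline is not only the old read.** The images themselves also serve as baseline, so re-scoring is not excluded, and extra baseline EM assessment is foreseen. True, but no re-score is required.

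**Worsening is not hidden.** Listing 16.2.6.2 would show it for each subject. True for the current SAP; the endpoint in Protocol 6.2.2 still reports responders only.

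**Conclusion.** The point holds within limits. The qualifying images and findings are the baseline, the on-treatment read is described as a comparison with pre-treatment images, and no masking of time point is specified. Reader expectation can therefore favour *decreased*; its size is unknown.

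For mesangial and endocapillary hypercellularity, and crescents in DDD, selection adds an excess of roughly 4–15 percentage points (0.6 to 2.1 of 14 subjects), falling to about 1 point when true activity is high. These figures rest on assumed activity distributions, equal glomerular counts at both biopsies and a single modelled feature. They do not apply to the other categories.

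The documents do not support saying that the reader is unmasked, that all five categories are biased towards response, or that masked reading would remove the chance effect.

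The practical weight is now small. No morphologic response proportion will be tabulated, and the documents do not say whether either treated subject had a Week 24 biopsy. The point bears on the protocol as designed and on how any decrease in the listing is read.

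**What to change.** In Protocol 12.4.2.1, state that for the endpoint the same central pathologist re-scores the stored images of both biopsies in random order, masked to subject and time point, and without the eligibility read or the local report details. In Protocol 6.2.2, report improved, unchanged and worsened counts for each category.

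State the limit in the text: this removes expectation bias and read error carried over from the qualifying read, but not regression to the mean from tissue sampling in the entry features, because the qualifying tissue remains the baseline. A control group or a prespecified minimum change would be needed to deal with that part.

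For the abbreviated report, add a footnote with the same caveat to Listing 16.2.6.2. With two treated subjects, masked random-order reading offers little, and the footnote is the useful step.

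Cost: one added reading session on images already stored, with no new biopsy and no new reader. The footnote costs next to nothing.
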